2 STUDY OBJECTIVES AND ENDPOINTS

All study objectives will be evaluated in subjects diagnosed with COVID-19.

Objectives	Endpoints
Primary	
To assess the efficacy of losmapimod compared with placebo for treatment of COVID-19 when administered concurrently with standard of care	Proportion of progressors to death or respiratory failure by Day 28
Secondary	
To evaluate the effect of losmapimod compared with placebo on clinical outcomes	
Clinical status by Days 7 and 14 as measured on the 9-point WHO ordinal scale (WHO 2020):
 
• (8) death• (7) ventilation plus additional organ support (vasopressors, renal replacement therapy, ECMO)• (6) Intubation and mechanical ventilation• (5) noninvasive ventilation or high-flow oxygen therapy• (4) oxygen therapy but not requiring high-flow or non-invasive ventilation• (3) hospitalized but not requiring oxygen therapy• (2) Discharged from the hospital but with limitation of activities• (1) Discharged from the hospital and without any limitation• (0) No clinical evidence of the disease
To assess the effect on clinical status of treatment with losmapimod compared with placebo	
Total number of study days free of oxygen supplementation by Day 28
 
Total number of study days in ICU by Day 28
 
Total number of study days hospitalized by Day 28
 
Total number of respiratory failure-free study days by Day 28

Fulcrum Therapeutics
Protocol FIS-001-2020

Losmapimod

Objectives	Endpoints
	Percentage of subjects discharged from the hospital by Day 28
To assess the effect on survival following treatment with losmapimod compared with placebo	All-cause mortality at Day 28 Number of study days alive by Day 28
To assess the safety and tolerability of losmapimod compared with placebo	Incidence of AEs and SAEs Incidence of clinically significant changes in laboratory parameters and vital sign measurements
To characterize changes in SARS-CoV-2 infection following treatment with losmapimod compared with placebo	Quantifiable viral RNA on Day 7

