4.2 Exclusion criteria

1. Inability to take oral medication at screening or baseline visit.
2. Evidence at screening or baseline of critical COVID-19 disease (eg, cardiac failure, septic shock or ARDS) or immediate need for intubation or mechanical ventilation per the judgment of the investigator.
3. Positive pregnancy test at screening for women of childbearing potential.
4. Lactating female at baseline for women of childbearing potential.
 - a. Note: a female will be considered eligible who is lactating at screening if she agrees to discontinue breastfeeding for the duration of the trial plus 14 days post last dose.
5. $\geq 5 \times$ upper limit of normal (ULN) for alanine or aspartate aminotransferases or total bilirubin $>1.5 \times$ ULN at screening or known history of Child-Pugh Class C, hepatitis B or C, or poorly controlled HIV infection. (Subjects with HIV infection who have normal CD4 counts may participate if they have been on a stable antiviral regimen for the 30 days prior to screening and are anticipated to remain on the regimen throughout the duration of the study.)
6. Glomerular filtration rate $<30 \text{ mL/min/1.73 m}^2$ at screening.
7. QTcF $>450 \text{ msec}$ for male or $>470 \text{ msec}$ for females or evidence of cardiac dysrhythmia at screening.
8. Significant history or evidence of clinically significant disorder, condition, current illness, illicit drug or other addiction, or disease that, in the opinion of the Investigator, would pose a risk to subject safety or interfere with the study evaluation, procedures, or completion.
9. Has been treated with immunomodulators or immunosuppressants including, but not limited to, interleukin (IL)-6 inhibitors, tumor necrosis factor (TNF) inhibitors, anti-IL-1 agents, and Janus kinase inhibitors, within 5 half-lives or 30 days, whichever is longer, prior to randomization, or plan to receive these agents any time during the study period.
10. Treatment with hydroxychloroquine/ chloroquine in the past 30 days or plan to receive these agents as part of investigational clinical trials or SOC any time during the study period.
11. Recent (within 30 days) or current participation in other COVID-19 therapeutic trials or expanded access programs.
12. Prior or current participation in COVID-19 vaccine trials.

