6.5.1 Vital signs

Evaluations of systolic and diastolic blood pressure, respiratory rate, and temperature will be performed throughout the study. In addition, oxygen saturation and FiO_2 will be assessed throughout the study. Oxygen administration (eg, room air or oxygen flow by nasal canula or facial mask) will be recorded. Vital signs will be performed after subjects have been supine for at least 5 minutes when possible.

Arterial blood gases may be performed if clinically indicated in some subjects but are not required for this study. If arterial blood gasses are measured, the results for arterial pressure of oxygen (PaO_2) should be reported at each measurement in the eCRF.

Clinically relevant findings found after study drug initiation and meeting the definition of an AE (new AE or worsening of previously existing condition) must be recorded.

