8.7 Secondary endpoints

Clinical status at Day 7 and Day 14:

Change in clinical status between baseline and post-baseline will be modelled using regression models appropriate for ordinal data, adjusting for stratification factors, sex, and baseline CRP. Details will be provided in the SAP.

Percentages for each category of the ranking scale will be tabulated by treatment arm, along with differences between treatment arms at each time point. The proportion of subjects for each of the items in the scale will be compared using an adjusted risk difference obtained from a regression model, adjusting for stratification factors, sex, and baseline CRP. Full details of the regression model will be provided in the SAP.

Total number of study days: (a) free of oxygen supplementation; (b) in ICU; (c) of hospitalization; (d) free of respiratory failure; (e) alive: For each endpoint (a) - (e), a Poisson regression model or a negative binomial model will be used to assess the relationship with treatment, adjusting for stratification factors, sex, baseline CRP and number of days on study (as applicable). Details of the model, including censoring rules, if any, will be provided in the SAP.

[figure not shown]
Percentage of subjects discharged from the hospital: percentages of subjects discharged from the hospital will be tabulated by treatment arm, along with differences between treatment arms. The proportion of subjects will be compared using an adjusted risk difference obtained from a regression model, adjusting for stratification factors, sex, and baseline CRP. Full details of the regression model will be provided in the SAP.

[figure not shown]
All-cause mortality at Day 28: percentages of subjects will be tabulated by treatment arm, along with differences between treatment arms, at each time point. The proportion of subjects will be compared using an adjusted risk difference obtained from a regression model, adjusting for stratification factors, sex, and baseline CRP. Full details of the regression model will be provided in the SAP.

Incidence of AEs/SAEs: will be summarized by system organ class and preferred term and by treatment arm using percentages.

Incidence of clinically significant changes: Percentage of subjects with clinically significant changes in laboratory parameters, ECG, and vital sign measurements will be computed for each treatment arm along with associated 2-sided 95% Clopper-Pearson CI.

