3 STATISTICAL METHODOLOGY

3.1 General Considerations

3.1.1 *Analysis Day*

Analysis day will be calculated from the date of first dose of study drug. The day of the first dose of study drug will be Day 1, and the day immediately before Day 1 will be Day -1. There will be no Day 0.

3.1.2 *Definition of Baseline*

Baseline is defined as the last measurement prior to the first dose of study drug.

3.1.3 *Summary Statistics*

Categorical data will generally be summarized with counts and percentages of subjects. The denominator used for the percentage calculation will be clearly stated. Continuous data will generally be summarized with descriptive statistics including n (number of non-missing values), mean (with its standard error), first quartile, median, third quartile, standard deviation, minimum, and maximum.

Where appropriate, descriptive statistics may be presented with 95% CI.

3.1.4 *Hypothesis Testing*

All statistical comparisons will be made using one-sided tests at $\alpha = 0.025$. All null hypotheses will be of no treatment difference, and all alternative hypotheses will be one-sided. Confidence intervals will be 2-sided with $\alpha = 0.05$ and reported to the same precision as the applicable summary statistic (e.g., mean), and standard error will be reported to one additional decimal place. P-values will be reported to four decimal places, with p-values less than 0.0001 reported as "<0.0001".

3.1.5 *Type I Error for Testing Key Study Endpoints*

The overall Type I error of the study will be controlled at 0.025 for 1-sided tests of hypotheses for the following key study endpoints, using a closed test procedure. The key endpoints will be tested in the fixed sequence procedure as the same sequence they are listed below. Assuming the analysis of the prior endpoint yields statistically significant treatment effect, the next key endpoint will be tested.

1. Proportion of progressors to death or respiratory failure by Day 28
2. Change in clinical status using the 9-point WHO scale at Day 14
3. Change in clinical status using the 9-point WHO scale at Day 7
4. Oxygen-free days by Day 28

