Percentages of subjects will be tabulated by treatment arm, along with differences between treatment arms, at each time point. The proportion of subjects will be compared using an adjusted risk difference obtained from a logistic regression model, adjusting for stratification factors, sex, and baseline CRP.

Standard survival analysis methods will be used as sensitivity analyses to compare the time to each of these clinical events of interest (death and respiratory failure) as well as the composite thereof. Specifically, the cumulative incidence rates between two groups at Day 28 will be compared, accounting for potential differential follow-up.

Incidence of AEs/SAEs by Day 28: will be summarized by system organ class and preferred term and by treatment arm using percentages.

Incidence of AEs/SAEs is calculated by the number of subjects who developed AEs/SAEs during the study divided by the sum of the number of subjects who completed the study and the number of subjects who died during the study period. (see above edit)

Incidence of clinically significant changes by Day 28: Percentage of subjects with clinically significant changes in laboratory parameters, ECG, and vital sign measurements will be computed for each treatment arm along with associated 2-sided 95% Clopper-Pearson CI.

Changes in the assessments will be considered as clinically significant if the Baseline assessment is not clinically significantly abnormal and there has been at least one occurrence of post-Baseline assessments with a clinically significant abnormal result by Day 28.

[figure not shown]
Death is not considered a form of missing data or censoring. The incidence of clinically significant changes is calculated by the number of subjects with clinically significant changes during the study divided by the sum of the number of subjects who completed the study and the number of subjects who died during the study period.

Clearance of quantifiable viral RNA by Day 7: percentages of subjects with clearance of quantifiable viral RNA will be tabulated by treatment arm, along with differences between treatment arms, at each time point. The proportion of subjects will be compared using an adjusted risk difference obtained from a logistic regression model, adjusting for stratification factors, sex, and baseline CRP.

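### The clinically significant change endpoint in SAP 3.4.2 counts only new-onset abnormality: worsening from a clinically significantly abnormal baseline cannot register, yet those subjects stay in the denominator

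*SAP*

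**What the plan says.** The objectives table in Protocol Section 2 names the endpoint as "Incidence of clinically significant changes in laboratory parameters and vital sign measurements". Protocol 8.7 adds ECG and gives the analysis: "Percentage of subjects with clinically significant changes in laboratory parameters, ECG, and vital sign measurements will be computed for each treatment arm", with a two-sided 95% Clopper-Pearson interval. Neither place sets a condition on baseline status or defines a change.

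SAP 3.4.2 supplies the definition, in two parts that must both hold. First, "Changes in the assessments will be considered as clinically significant if the Baseline assessment is not clinically significantly abnormal". Second, "there has been at least one occurrence of post-Baseline assessments with a clinically significant abnormal result by Day 28". SAP 3.1.2 fixes the reference point: "Baseline is defined as the last measurement prior to the first dose of study drug". The count of subjects with such a change is then "divided by the sum of the number of subjects who completed the study and the number of subjects who died during the study period". The end of SAP 3.4.2 adds that this endpoint will be compared between arms in a similar way to the primary endpoint.

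**The concern.** The trial enrols acutely ill inpatients, some of whom will have abnormal findings before the first dose. Criterion 5 in Protocol 4.2 sets its limits as multiples of the "upper limit of normal (ULN) for alanine or aspartate aminotransferases or total bilirubin": aminotransferases are excluded only at or above 5 × ULN, and bilirubin only above 1.5 × ULN. Suppose a subject enters with ALT at 4 × ULN, the investigator rates it clinically significant, and it then passes 8 × ULN, a level Protocol 3.4.1 lists for considering discontinuation. That subject counts as having no change in ALT.

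Two things are at stake. A reader may take the table as covering all clinically significant deterioration when it covers only new onset. And because subjects who cannot be events are kept in the denominator, even the new-onset percentage is too low.

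**Working it through.** **Reading the rule.** By the rule's logic, with CS meaning clinically significant(ly):

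| Baseline | Worst post-baseline result | Counted? | In denominator? |
|---|---|---|---|
| Normal | CS abnormal | Yes | Yes |
| Abnormal, not CS | CS abnormal | Yes | Yes |
| CS abnormal | CS abnormal and worse | No | Yes |

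(The last column assumes the subject completes or dies.) Only the third row is affected. The ECG scale in Protocol 6.5.4 has a separate class for abnormal findings that are not clinically significant, and such a baseline does not block counting.

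**Size.** The plan states no expected incidence, no share of CS-abnormal baselines and no numerical criterion for clinical significance, so there is no figure to reproduce. The following is illustration only. Inputs: N = 205 per arm (SAP 2.2.4), all assumed to complete or die; f = assumed share with a CS-abnormal baseline on a parameter; r = assumed rate of a new CS abnormality among the rest.

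Barred subjects B = f × N. Events x = r × (N − B). SAP percentage = x / N, approximately (1 − f) × r. At-risk percentage = x / (N − B). Counts are rounded to whole subjects.

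| r | f | B | x | SAP: x/205 (95% CI) | At-risk denominator (95% CI) |
|---|---|---|---|---|---|
| 20% | 0% | 0 | 41 | 20.0% (14.8–26.1) | 41/205 = 20.0% (14.8–26.1) |
| 20% | 10% | 20 | 37 | 18.0% (13.0–24.0) | 37/185 = 20.0% (14.5–26.5) |
| 20% | 20% | 41 | 33 | 16.1% (11.3–21.9) | 33/164 = 20.1% (14.3–27.1) |
| 20% | 30% | 62 | 29 | 14.1% (9.7–19.7) | 29/143 = 20.3% (14.0–27.8) |
| 10% | 0% | 0 | 20 | 9.8% | 20/205 = 9.8% |
| 10% | 30% | 62 | 14 | 6.8% | 14/143 = 9.8% |

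At r = 20% and f = 30%, the interval under the SAP rule ends at 19.7%, below the rate assumed for subjects at risk. The largest percentage the rule can report is (N − B)/N: 90.2%, 80.0% and 69.8% for f = 10%, 20% and 30%.

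With the same f in both arms, a between-arm difference shrinks by the factor (1 − f). An assumed 10-point difference among subjects at risk is reported as 0.9 × 10 = 9, 0.8 × 10 = 8 or 0.7 × 10 = 7 points.

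**Where else worsening could appear.**
- SAP 3.5.1: TEAEs include worsening of a pre-existing condition. QTc prolongation and potential drug-induced liver injury are AESIs and are summarised.
- SAP 3.5.2: laboratory change from baseline by visit and out-of-range counts carry no baseline condition. An out-of-range count treats 4 × and 8 × ULN alike. The by-visit statistics include a maximum, so an extreme value shows, but not how many subjects worsened or from what level. No shift table is planned.
- SAP 3.5.3: similar summaries for blood pressure, pulse, temperature, oxygen saturation and inspired oxygen. Respiratory rate is not named in the change-from-baseline text.
- SAP 3.5.4: apart from this endpoint, ECG values are only listed.
- Protocol 7.1.8: potential liver injury also needs bilirubin at or above 2 × ULN and alkaline phosphatase below 2 × ULN, so an isolated ALT rise does not qualify.

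**Unit.** The SAP does not say whether the baseline condition applies per parameter or to a whole panel. Read per panel, one CS laboratory value at baseline would bar every laboratory parameter for that subject.

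**The case against.** The strongest reply is that new onset is an ordinary way to define incidence, that the rule uses pre-dose status and is identical in both randomised arms, and that worsening belongs to adverse event reporting. Protocol 6.5.1 requires that clinically relevant findings "meeting the definition of an AE (new AE or worsening of previously existing condition) must be recorded", and Protocol 6.5.5 says the same for laboratory results. A rise from 4 to 8 × ULN would normally be reported, and would also appear among TEAEs leading to discontinuation if drug were stopped for it.

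Most of this stands, and it rules out several stronger readings a reader might reach:
- That worsening is lost to the whole analysis. It is lost to this endpoint only.
- That any abnormal baseline is barred. Only a CS-abnormal one is.
- That ECG is the main problem. Protocol 4.2 excludes QTcF above 450 msec (men) or 470 msec (women) and dysrhythmia at screening. The schedule has no Day 1 ECG, so the screening tracing will usually be the baseline and few subjects should be barred.
- That the SAP made an undeclared protocol change. The protocol leaves change undefined and assigns implementation to the SAP, so the absence of this item from SAP Section 6 is not clearly an omission.
- That an excess of harm on losmapimod would be hidden. No document gives a rate of worsening in either arm.

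What does not stand is that the other summaries fill the gap. Adverse events depend on the investigator's report, and the laboratory and vital-sign tables are descriptive and do not grade worsening. This endpoint is the only safety laboratory, ECG and vital-sign analysis with a planned comparison between arms. Nor does the reply address the denominator.

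**Conclusion.** The point holds as a limitation of one secondary safety endpoint. It measures new-onset CS abnormality without saying so, cannot register worsening from a CS-abnormal baseline, and understates new onset by roughly the factor (1 − f). That factor follows from the definition; its value does not, because f is not in the documents, and the range of 10% to 30% above is an assumption. If f is near zero for a parameter, the effect is negligible. The comparison between arms remains a valid one for new onset, though attenuated. The primary endpoint and the fixed testing sequence in SAP 3.1.5 are unaffected.

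**What to change.** In SAP 3.4.2:

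1. State that the rule applies per parameter.
2. Label the endpoint as new-onset clinically significant abnormality.
3. Within the completers-plus-deaths set, restrict each parameter's denominator to subjects without a CS-abnormal baseline for that parameter, and report how many are left out in each arm.
4. Add, by arm, shift tables from baseline category to worst post-baseline category for ALT, AST, bilirubin, creatinine and QTcF, with the categories fixed in the SAP in advance. Several cut-points already appear in Protocol 3.4.1, 4.2 and 7.1.8 for the liver tests and QTcF. None is given for creatinine, so one must be specified.

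The shift tables use values the protocol already collects. A separate investigator judgement that worsening was clinically significant is not proposed, because the documents do not show that it is collected. The cost is a few lines of SAP text and a little more programming. The reported percentages may rise in both arms.

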⁴ PK assessments will be performed as a substudy in all sentinel subjects. For those subjects requiring dialysis, a single pre- and post-dialysis PK should be obtained for review by the DMC to decide if dose adjustment is needed. PK should be measured weekly for 2 weeks at C_{max} (4-5 hours post dose) for subjects with renal insufficiency when possible.

⁶ Assessments for clinical/respiratory status, progression, and safety serum chemistry and hematology tests to be performed and samples to be collected while hospitalized based on standard-of-care local laboratory assessments and after discharge from the hospital by home visit or outpatient clinic visit or telemedicine call. For subjects who are discharged to home or other outpatient setting after initial hospitalization, the assessments and laboratory samples can be obtained less often but not less than at least once weekly. CRP result required to determine eligibility are based on local laboratory results at screening.

⁷ Viral load testing will be collected daily for the first 4 days using central testing in the first 10 enrolled subjects as part of the sentinel safety assessment at select sites. For all subjects, including the sentinel subjects, swabs, saliva, or other sample collection (as specified in the Study Manual) for central viral load testing will be collected on D1 pretreatment and on D7 or earlier if being discharged from the hospital prior to D7.

Fulcrum Therapeutics
Protocol FIS-001-2020

Losmapimod

⁸ Vital signs will be performed after subjects have been supine for at least 5 minutes when possible. Vital signs to include oxygen saturation; PaO₂ should be recorded if available from blood gases obtained as part of SOC; oxygen administration should also be recorded (eg, room air or oxygen flow by nasal canula or facial mask or endotracheal tube). For subjects who are discharged to home or other outpatient setting after initial hospitalization, assessments may be obtained less often but at least once per week in the outpatient clinic or at home.

⁹ Height assessed at screening only; can be by self-report or from medical records. Weight is an actual recording.

¹⁰ Urinalysis will be performed during the study period only on Day 7 and on any other day only if clinically indicated.

¹¹ Pregnancy testing to be conducted within 72 hours of the first dose of study treatment.

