2 STUDY OVERVIEW

2.1 Objectives and Endpoints

| Objectives | Endpoints |
|---|--|
| Primary | |
| To assess the efficacy of losmapimod compared with placebo for treatment of COVID-19 when administered concurrently with standard of care | Proportion of progressors to death or respiratory failure by Day 28 |
| Secondary | 
To evaluate the effect of losmapimod compared with placebo on clinical outcomes
 
Clinical status by Days 7 and 14 as measured on the 9-point WHO ordinal scale:
 
• (8) death• (7) ventilation plus additional organ support (vasopressors, renal replacement therapy, ECMO)• (6) Intubation and mechanical ventilation• (5) noninvasive ventilation or high-flow oxygen therapy• (4) oxygen therapy but not requiring high-flow or non-invasive ventilation• (3) hospitalized but not requiring oxygen therapy• (2) Discharged from the hospital but with limitation of activities |

| | |
|---|---|
| | 
• (1) Discharged from the hospital and without any limitation• (0) No clinical evidence of the disease |
| To assess the effect on clinical status of treatment with losmapimod compared with placebo | Total number of study days free of oxygen supplementation by Day 28 Total number of study days in ICU by Day 28 Total number of study days hospitalized by Day 28 Total number of respiratory failure-free study days by Day 28 Percentage of subjects discharged from the hospital by Day 28 |
| To assess the effect on survival following treatment with losmapimod compared with placebo | All-cause mortality at Day 28 Number of study days alive by Day 28 |
| To assess the safety and tolerability of losmapimod compared with placebo | Incidence of AEs and SAEs Incidence of clinically significant changes in laboratory parameters and vital sign measurements |
| To characterize changes in SARS-CoV-2 infection following treatment with losmapimod compared with placebo | Quantifiable viral RNA on Day 7 |
| | |

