2.2.4 Sample Size Determination

The primary efficacy endpoint of this study is the proportion of subjects who progress to death or respiratory failure by the end of study (Day 28). It is estimated that approximately 30% of enrolled subjects receiving SOC plus placebo will attain this endpoint. It is assumed that losmapimod will improve the primary endpoint by 40% over placebo. On the basis of these assumptions, a total of up to 410 subjects randomized to the losmapimod arm or the placebo arm in a 1:1 ratio (205 subjects in the losmapimod arm and 205 subjects in the placebo arm) will yield approximately 80% power in a 1-sided test at the 2.5% significance level.

The sample size estimate assumes an IA will be conducted after approximately 206 subjects (103 in the losmapimod arm, and 103 in the placebo arm) have completed the Day 28 visit, to assess early futility, using the rules specified in Section 5.1.

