3.1.8 Handling of Dropouts and Missing Data

All missing or incomplete safety and PD data, including dates and times, will be treated as such. Missing test results or assessments will not be imputed, and as such, are assumed missing completely-at-random (MCAR).

For laboratory data, values below the limit of quantitation (recorded as “< LLQ”) will be set to half that limit.

For the analysis of hospital-free and ICU-free days, subjects who die prior to the analysis time point will have post-death days considered to be not hospital-free and not ICU-free.

Adverse events with missing start dates will be considered as treatment-emergent unless the partial date excludes that possibility, e.g., the adverse event month is prior to the first dose of study drug. Otherwise, the first day of the month will be used to impute missing start days and January will be used to impute missing start months. For example, if the first dose of study drug was on January 8, 2021 and an adverse event started in January 2021 with missing day, the start date will be imputed as the first dose date (January 8, 2021) and this adverse event will be considered as treatment-emergent. In the same example, if another adverse event has start month of December 2020 with missing day (before the first dose date of January 8, 2021), its start date will be imputed as December 1, 2020 and will not be considered as treatment-emergent.

Subjects who terminate the study prior to the analysis time point, not due to death, will be considered as missing for the analysis of key efficacy endpoints. Missing data in each treatment arm will be imputed using the observed data in their respective arm under the missing at random (MAR) assumption. Multiple imputation (MI) will be performed using the fully conditional specification (FCS) model. The imputation model will include the stratification factors, sex, and baseline CRP.

The handling of missing data for the key efficacy endpoints are outlined as the following:

1. Primary endpoint: patients whose status could not be ascertained (lost-to-follow up, etc.) will be imputed using multiple imputation approach.
2. Change in Clinical Status at Days 7 and 14: missing clinical status at the post-baseline timepoint will be imputed using multiple imputation approach.

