3.3.4 Demographic and Baseline Characteristics

The following demographic and baseline characteristics will be summarized:

- Age (years) and age categories (<65 years, \geq 65 years)
- Sex
- Race
- Ethnicity
- Height (cm)
- Weight (kg)
- Body mass index (BMI) (kg/m^2) and BMI categories (<30 kg/m^2 , \geq 30 kg/m^2)
- Requirement for oxygen at randomization (yes, no)
- Chest imaging
- COVID-19 diagnosis
- Baseline CRP by central lab (Day 1) and categories
- Baseline IL-6 by central lab (Day 1)
- Viral load by central lab PCR (Day 1 and Day 7, unless sentinel group or ET)
- Region (US, Ex-US)

Demographic and other baseline characteristics will be summarized using descriptive statistics for the treatment group and overall for all randomized subjects.

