Change from baseline in viral RNA will be summarized by treatment arm and also analyzed using an analysis of covariance (ANCOVA) model with fixed effects of treatment, and stratification factors, sex and baseline CRP as covariates.

Death is not considered a form of missing data or censoring. The proportion of subjects with clearance of quantifiable viral RNA by Day 7 is calculated by the number of subjects with clearance of quantifiable viral RNA by Day 7 divided by the sum of the number of subjects who is in study by Day 7 and the number of subjects died by Day 7.

The endpoint of comparing percentage of subjects discharged from the hospital, all-cause mortality by Day 28, incidence of AEs/SAEs, incidence of clinically significant changes, and percentage of subjects with clearance of quantifiable viral RNA by Day 7 between treatment groups will be analyzed similarly as the primary endpoint.

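### The ANCOVA for change in viral RNA leaves out baseline viral RNA and names no measurement scale

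*SAP*

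**What the plan says.** SAP 3.4.2 gives two analyses of viral RNA. The first is the proportion of subjects who clear quantifiable RNA by Day 7, compared by logistic regression with the stratification factors, sex and baseline CRP. Protocol 8.7 plans that analysis too. The second appears only in the SAP: "Change from baseline in viral RNA will be summarized by treatment arm", and is to be "analyzed using an analysis of covariance (ANCOVA) model with fixed effects of treatment, and stratification factors, sex and baseline CRP as covariates". The covariate list is complete as printed, and baseline viral RNA is not in it. Neither the SAP nor Protocol Version 3.0 names a log or log10 scale for viral RNA.

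The missing covariate is collected. Protocol Version 3.0, Table 1, footnote 7, says that in all subjects samples for "central viral load testing will be collected on D1 pretreatment and on D7 or earlier" if discharge comes first. SAP 3.1 fixes which value counts: "Baseline is defined as the last measurement prior to the first dose of study drug". SAP 3.3.4 includes among the baseline characteristics "Viral load by central lab PCR (Day 1 and Day 7, unless sentinel group or ET".

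SAP 3.1.8 says that laboratory values below the lower limit of quantitation (LLQ) "will be set to half that limit". It does not mention viral RNA or a transformation.

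SAP 2.1 lists the endpoint as "Quantifiable viral RNA on Day 7" under the secondary objectives. It is not one of the four endpoints in the fixed sequence of SAP 3.1.5.

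**The concern.** The model adjusts for the baseline of a different variable, CRP, but not for the baseline of its own response. How far a subject's viral RNA can fall depends on where it starts. A subject near the quantitation limit has almost no room to fall, and the half-LLQ rule sets a hard floor. A subject with a high load can fall by several logs. Subtracting the baseline does not remove this dependence: unless ρ times the Day 7 SD happens to equal the Day 1 SD, the change score still correlates with the starting value.

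There are two consequences. A chance imbalance in Day 1 load enters the treatment difference in part, and the residual variance is larger than it needs to be. Separately, a result on copies and a result on log10 copies can differ greatly, so leaving the scale open leaves the analysis incompletely pre-specified.

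**Working it through.** **The plan's own figure.** The documents give no power or precision figure for viral RNA. Their only power statement, in SAP 2.2.4, concerns the primary endpoint: 205 per arm "will yield approximately 80% power in a 1-sided test at the 2.5% significance level". It reproduces. With rates 0.30 and 0.18, unpooled variance 0.30 × 0.70 + 0.18 × 0.82 = 0.3576, and the SAP 5.1 bounds of −0.67873 at 103 per arm and −1.91358 at 205 per arm, power is 0.802 and type I error 0.0250. Nothing below changes those numbers.

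**Set-up for viral RNA (log scale).** Take the Day 1 SD as 1, let k = SD(Day 7)/SD(Day 1), and let ρ be the Day 1 to Day 7 correlation. Read both as values after adjustment for the covariates already listed. The documents give neither.

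- Variance of the change score without baseline in the model: 1 + k² − 2ρk.
- Variance with baseline in the model: k²(1 − ρ²).
- Difference: (1 − ρk)². This is never negative, so in large samples adding the baseline cannot raise the variance.
- Proportional reduction: (1 − ρk)² / (1 + k² − 2ρk). With k = 1 this is (1 − ρ)/2.

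Reduction in variance from adding the baseline:

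| k | ρ = 0.3 | ρ = 0.5 | ρ = 0.7 |
|---|---|---|---|
| 0.8 | 50% | 43% | 37% |
| 1 | 35% | 25% | 15% |
| 1.25 | 22% | 11% | 2% |
| 1.5 | 13% | 4% | under 1% |

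As an example, for k = 1.25 and ρ = 0.3: (1 − 0.375)² / (1 + 1.5625 − 0.75) = 0.3906/1.8125 = 0.216.

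**What this means with equal SDs (k = 1) and both values available in all 410 subjects.** Without the baseline, 410 subjects carry the information of 410 × (1 + ρ)/2, which is 266.5, 307.5 and 348.5 at ρ = 0.3, 0.5 and 0.7. Consider an effect that has 80% power, one-sided 0.025, with the baseline in the model. Its power without the baseline is Φ(2.802 × √[(1 + ρ)/2] − 1.960):

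- ρ = 0.3: Φ(2.259 − 1.960) = 62%
- ρ = 0.5: Φ(2.426 − 1.960) = 68%
- ρ = 0.7: Φ(2.583 − 1.960) = 73%

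**Chance imbalance.** If the arms differ by d in mean Day 1 load, the expected contribution to the difference in change is −(1 − ρk)d. With k = 1 that is 70%, 50% and 30% of d at ρ = 0.3, 0.5 and 0.7. With the baseline in the model, the contribution is removed.

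**The case against.** The strongest reply is that the cost is unknown and may be small. The change score already uses the baseline by subtraction. At ρ = 0.8 with equal SDs the saving is 10%, and with a Day 7 SD 1.25 times that of Day 1 and ρ = 0.7 it is 2%. Randomisation keeps the estimate unbiased in expectation, so this is a matter of efficiency and not validity. All of that stands. It limits the size of the point without removing it, because the adjustment is at worst neutral. The half-LLQ floor also compresses the low end of the Day 7 values, which pushes k down, where the saving is larger.

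Several stronger readings are tempting, and the documents do not support them.

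- *The analysis is on raw copies and has almost no power.* In an illustrative simulation (log10 SD 1.0 to 1.5, mean fall 2 log10, ρ 0.3 to 0.7, effect set for 80% power with the log10 model that includes baseline), raw-scale change without baseline had about 1% power, against 62% to 74% for log10 change without baseline. But the SAP does not prescribe raw copies; it leaves the scale unstated. SAP 7 puts detailed programming specifications in a separate document, and the SAP's code appendices are not in the text available. The simulation shows why the scale should be stated, not that the planned analysis fails.
- *The Day 1 sample was taken to give this precision.* The protocol states when it is collected, not why.
- *This is the only quantitative analysis of viral RNA.* That cannot be confirmed. SAP numbering runs from 3.4.2 to 3.4.4, and SAP 3.1.7 gives a covariance rule for a repeated-measures model that the visible text never specifies.
- *A baseline imbalance passes straight into the result.* It enters at about 1 − ρ with equal SDs, not in full.

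**Conclusion.** The point holds as an avoidable loss of efficiency and a gap in specification. The covariate list omits baseline viral RNA and the scale is not named; both are plain from the text. With equal SDs on the log scale the omission costs 35%, 25% or 15% of the variance at ρ = 0.3, 0.5 or 0.7, and less if Day 7 values are clearly more spread than Day 1 values. Those sizes rest on assumed ρ and SDs and on every subject having both samples. Only the direction is certain. The consequence is confined to a secondary analysis outside the alpha-controlled sequence, and nothing in the primary analysis depends on it.

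**What to change.** Replace the model sentence in SAP 3.4.2 with: *Change from baseline in log10 viral RNA will be analysed by ANCOVA with treatment, baseline log10 viral RNA, stratification factors, sex and baseline CRP. Values below the LLQ will be set to half the LLQ before the log transformation.*

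The cost is that one change of text. It needs no new data and drops no subject, because a change score already requires the Day 1 value.

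Leave the clearance model as it is. Protocol 8.7 fixes its covariates as the stratification factors, sex and baseline CRP. SAP 3.4.2 counts everyone in the study by Day 7, plus deaths by then, in its denominator. Adding baseline load there would depart from the protocol and could drop subjects who lack a Day 1 value.
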